- ii. Evaluate if there is a significant difference in operative duration (time) and intra-operative cost for patients undergoing EGD vs.
 ViSiGi® 3D suction device calibration during sleeve gastrectomy
- iii. Assess longer post-operative outcomes including GERD symptom severity and weight loss
 - 1. GERD-HRQL questionnaire pre-op and post-op 2 (+/- 2 months) & 12 mo (+/- 12 months) (4)
 - 2. Weight loss mean % total body weight loss, mean % EWL, mean % change in BMI (12 mo, +/- 12 months)

3. Background

Previous studies have shown that compared to a standard weighted rubber bougie (RB), using a suction calibration device (SCD) results in a straighter staple line compared to a twisted and corkscrewed staple line (1); no studies to date have compared upper endoscopy calibration to SCD for SG. Due to the straighter, and therefore shorter, staple line, the hypothesis is the surgeon should be able to use fewer staple loads with a SCD. Bariatric staple loads are expensive, so a reduction in their use has the potential for savings to the hospital.

The study will also look at how a suction calibration system can create savings for the hospital in OR time and scope processing costs. As previously mentioned, the SCD may require fewer stapler load firings; it also eliminates the need for placing multiple tubes in to the stomach as well as an upper endoscopy leak test and therefore saves the OR staff time and may decrease operative duration. The SCD is also disposable which

eliminates the need for reprocessing. Current estimates for reprocessing an endoscope are around \$200 (2) thus the SCD use may decrease operative cost.

It is also hypothesized that a misaligned smaller sleeve after a LSG procedure can increase the prevalence of post-operative GERD due to removal of the fundus and twisting of the sleeve (3). A straighter, correctly calibrated sleeve should decrease the prevalence of GERD in patients. Therefore, the study will also look at the prevalence of pre-operative vs. post-operative GERD symptoms in patients who are undergoing LSG with endoscopic calibration vs. SCD.

4. Study Intervention/Investigational Agent

	Pre-operative period & Bariatrical Surgical consult	Day of Surgery (LSG)	Immediate Post-op follow-up (3 weeks) (+/- 2 weeks)	2mo post op f/u (+/- 2 months)	12 mo post op f/u (+/- 12 months)
Attg Surgeon or Surgical house staff research team members	Assess candidacy of patients for enrollment in study *Patients to be randomized into either EGD vs ViSiGi calibration sleeve gastrectomy *Pre-op education on ViSiGI usage via rep and online videos, instruction sheet for surgeons involved	EGD vs ViSiGi device usage for sleeve *No SPECIMEN COLLECTED *Standardize surgeon technique *Fill out Powernote template collecting all intraop data	Assess for complicati on & document in Exemplo	*medical bariatricia n f/u at 2mo *obtain cost data	Assess long- term weight loss, Compile tables, figures etc for abstract and manuscript generation
Study coordinator	Enroll, research consent process, administer	Ensure powernotes are		GERD- HRQL (in	GERD-HRQL (in person or phone)

	baseline GERD- HRQL, notify data analyst *Save hard copy of consent, paperwork in MOT7	done collection intraop data *notify data analyst		person or phone)	
Data Analyst	Enter patient as enrolled in Exemplo data base along with PHI, demographics, etc.	Enter OR date in Exemplo database along with operative duration and stapler information (HER op note, PowerNote with template for all pertinent data)	Assess for complicati on in EHR	EHR review for any 30- day post- op issues, GERD data entry, enter cost data as able	Query MBSAQIP for any post-op issues & weight loss data, enter GERD data entry, Assist w/ tables, figures etc for abstract and manuscript generation
Statistician	NA				TBD

5. Procedures Involved

- Pre-operative period & Bariatrical Surgical consult (usually 1-2 mo prior to surgery) period:
 - Assessing candidacy for study enrollment, research consent process, surgeon education on device, and GERD-HRQL for diagnostic and research purposes
 - Patients will be randomized to either the EGD vs. the ViSiGi device for sleeve gastrectomy calibration
 - o Neither the surgeon nor patient will be blinded to the device used
 - Patients will find out if they are in the EGD vs. ViSiGi device group preoperatively
- Day of surgery = Postop Day zero (POD0)
 - Use of EGD vs. ViSiGi calibration for sleeve intended for therapeutic and research purposes for surgeon

- Risks/discomforts of EGD and ViSiGi device are comparable. Using a ViSiGi device is similar to both a standard weighted bougie and an EGD calibration technique. The ViSiGi device is similar to a gastroscope in that they both have suction, calibration, and leak testing capabilities. The benefit of the ViSiGi device is that it obviates the need for doing an EGD during sleeve gastrectomy, is single patient use and thus does not require reprocessing, and doesn't require a scope tower to operate it. Potential benefits of using the ViSiGi device (in lieu of endoscopic calibration) in order of highest probability are as follows: 1) less staple loads, 2) shorter OR time, 3) reduced cost, 4) decreased post-op GERD rates.
- Data analyst and study coordinator to have research roles at this time
- Immediate post-op follow-up 3 weeks after surgery (+/- 2 weeks) to 12 months out (+/- 12 months)
 - Assessments made by surgeon will be for diagnostic, therapeutic and research purposes as appropriate
 - Study coordinator and data analyst will function in research roles only
 - Goal in this period is predominantly research purposes only
 - Due to constraints from COVID-19 and decreased in-person follow-up, the 12-month assessment time frame will be extended to 24 months post-surgery to help gather GERD-HRQL and weight loss data
 - a. What type of information will be collected:
 - i. See above table
 - ii. Demographic and clinical variables will be collected at (baseline) including age, gender, race, BMI, smoking status, functional status, and medical comorbidities:
 - 1. EHR
 - 2. MBSAQIP
 - 3. Baseline GERD-HRQL scores (standardized questionnaire)
 - iii. Intra-operative/procedure data (i.e. type of stapler used, # staple load firings, length and color stapler loads, etc.)
 - 1. EHR
 - 2. Research data sheets
 - iv. Post-operative data & assessment
 - 1. EHR
 - 2. MBSAQIP (30-day outcomes and weight loss outcomes)
 - 3. Cost data (administrative data) from internal databases
 - 4. GERD-HRQL scores (standardized questionnaire)

6. Inclusion and Exclusion Criteria

Patients selected for this study will be adults, 18 years old or older, who have already agreed with their surgeon that LSG is the best choice for them. Patients will be excluded by the following criteria;

- Subjects with prior gastric surgery or bariatric surgery (including prior adjustable gastric band and/or sleeve gastrectomy).
- Concomitant hiatal surgery
- Paraesophageal hernia at time of surgery
- Any subject with prescribed immunosuppressive drugs.
- In the opinion of investigator, subject is not eligible to participate in the study.
- If patient is a female and becomes pregnant at any time during the study duration

7. Local Number of Participants

There is no additional screening for the study that the patient would already be subject to if they were not part of the study. There will be 50 patients undergoing LSG with an endoscope and 50 patients undergoing LSG with a suction calibration system. Patients will be assigned randomly to each group.

8. Recruitment Methods

9. Subjects will be identified by the 1) treating physician/surgeon and/or her clinical staff or 2) the study staff reviewing clinic and/or hospital admissions. Risk to Participants

The risk for participating in this study is expected to be minimal and equivalent to standard peri-operative morbidity and mortality associated with sleeve gastrectomy. Moreover, patient safety and risk profiles are expected to be similar between the endoscopic vs. suction device calibration techniques. A rare complication associated with laparoscopic bariatric is tube/probe stapling during sleeve gastrectomy. Given that the ViSiGi device is a plastic tube it could potentially be stapled across during gastrectomy or cause other trauma to the stomach or esophagus with intra-operative manipulation during sleeve gastrectomy. It is also possible for a gastroscope to be stapled across during gastrectomy and to cause mucosal trauma with manipulation and suctioning during sleeve gastrectomy. Again, the overall risk directly associated with intra-operative use of either the ViSiGi or endoscopic devices during sleeve gastrectomy risk anticipated to be minimal (< 1%) and similar between groups.

10. Potential Benefits to Participants

This study, by its nature, will be focusing on bariatric surgery and therefore people with obesity who meet standard NIH criteria for weight loss procedures like LSG (5). The information from this study may help the community by giving the hospital information on ways to more effectively and efficiently perform LSG.

11. Compensation to Participants

There will be no patient reimbursement for participation in this study.

12. Data Management and Confidentiality

Data for this study will be recorded on a secure password-protected electronic database called **Exemplo**. Data entry will be done by study investigators and/or data analysts who are part of the approved IRB team. Unidentified data may be shared with the sponsor, Boehringer Laboratories LLC.

Data analysis will be done by internal or externally hired statisticians on de-identified data on spreadsheets downloaded from **Exemplo**.

Separate intra-operative data will be collected from the EHR either via the Operative Note or via standardized PowerNote templates (**if available**) to help capture data pertinent during sleeve gastrectomy including the following:

- 1) Patient Full Name: pre-populated/pull from eEMR
- MRN: pre-populated/pull from eEMR
- 3) **Date of surgery**: pre-populated/pull from eEMR
- 4) **Primary Surgeon**: pre-populated/pull from eEMR
- 5) **Stapler used**: Echelon Flex Powered 60mm stapler, Endo GIA 60 mm Universal Stapler XL; Other (free text)
- 6) **Distance from pylorus for 1**st **stapler firing**: Free text for centimeters
- 7) **Calibration device**: EGD/Standard Weighted Bougie Tapered/Standard Weighted Bougie Blunt/ViSiGi device/Other (free text)
- 8) Calibration device size: free text for French
- 9) Total number of stapler load firings: free text number
- 10) **Length of stapler loads used** (list number): 60 mm(free text number or click n/a); 45 mm (free text number or click n/a); other (free text)
- 11) **Number, order & color of stapler loads** (first to last; i.e. 2 green, 2 gold, 1 blue): free text
- 12) Use of Seam Guard reinforcement for stapler loads: yes/no
 - a. If yes, were all stapler loads reinforced? Yes/no; other (free text)
- 13) Other procedures performed:

- a. Plication/imbricating suture to sleeve: yes/no; other (free text)
- b. Pexy of omentum to sleeve: yes/no; other (free text)
- c. Clipping of sleeve staple line: yes/no; other (free text)
- d. Oversewing staple line: yes/no; other (free text)
- e. Fibrin glue to staple line: yes/no; other (free text)
- f. Any other procedures?: free text

14) **EGD done**: yes/no

- a. If yes, any abnormal findings: yes/no; other (free text)
- b. If abnormal findings, please list any interventions done: free text
- 15) Miscellaneous Notes: free text

13. Statistical Analysis

There will be 50 patients undergoing LSG with an endoscope and 50 patients undergoing LSG with a suction calibration system. Both methods are clinically accepted and approved methods of performing the procedure. The target enrollment will be 125 to account for attrition due to screen failures, early withdrawals, etc. For this study we use a randomized block design (RBD) to assign participants to one of two sleeve groups. In a RBD we divide participants into subgroups called blocks (e.g. gender, race, etc.), such that the variability within blocks is less than the variability between blocks. Then, subjects within each block are randomly assigned to treatment conditions (i.e. SG with EGD or SG with ViSiGi device). The purpose of the RBD is to help reduce variability within treatment conditions and potential confounding from blocking factors, producing a better estimate of treatment effects. We are adequately powered to detect a mean difference in stapler load firings of 0.4 between groups assuming a standard deviation of 0.7, which is consistent with our institutional sleeve gastrectomy experience. After all cases have been performed statistical methods will be implemented to determine any difference in outcomes. An initial approach will focus on a pairwise analysis (t-test) between the ViSiGi and EGD calibration groups for each of the primary and secondary aims. A more comprehensive multivariate analysis factoring in demographic and clinical variables will be performed to further delineate significant differences in the 2 sleeve gastrectomy methods. In the unlikely situation that an adverse event occurs, the event will be inspected to determine if an early stoppage is necessary.

14. Provisions to Monitor the Data to Ensure the Safety of Participants

All methods used in this study for performing sleeve gastrectomy are already approved and clinically accepted. Validated users of the device will be attending surgeons who have been trained using the ViSiGi device via online video-based education

(https://www.youtube.com/watch?v=zDhc-1fr32E), review of the manufacturer instructions for use (IFU) sheet below:

(chromeextension://oemmndcbldboiebfnladdacbdfmadadm/https://www.boehringerlabs.com/wp-content/uploads/2018/09/5232009.pdf) as well as in-person education via representatives from Boehringer Laboratories, LLC.

All surgeons will be required to complete the video-based module and review the IFU sheet prior to using the ViSiGi device.

The PI will be responsible for ensuring participants' safety on a weekly basis as cases are performed (sleeve gastrectomies are not always done every week) and for reporting serious Adverse Events (AEs) and Unanticipated Problems (UPs) to his or her Institutional Review Board (IRB) and the monitoring body with the help of the study coordinator. The study coordinator and/or PI will prepare reports that list AEs, serious AEs, deaths, and disease-or treatment-specific events required for MB review in order to ensure good clinical care and identify any concerning trends. The Monitoring Body (MB) will act in an advisory capacity to the PI to monitor participant safety, evaluate adverse events and progress of the study. The MB will constitute two surgeons who are not directly involved in the study protocol but participate in the care of bariatric patients at Emory University Hospital Midtown and will to review the safety data annually.

The PI will be informed of serious AEs as soon as they occur by Co-Investigators (i.e., surgeons performing sleeve gastrectomy) and/or the study coordinator and notify the MB within 48 hours of becoming aware of the event. The PI will report serious AEs and UPs to his or her IRB within 5 business days of becoming aware of the event. Events constituting UPs include calibration device malfunctions such as a piece or component of the device breaking off into the stomach during manipulation, failure of the device to adequately perform a leak test, or contamination or damage to the device such that it cannot be appropriately used. Specific triggers for an ad hoc review or initiation of the process of an ad hoc review will occur if there are unforeseen deaths or if there is a serious AE including stapling across a calibration device during sleeve gastrectomy or other serious device malfunction leading to patient injury. At any point during the study time period, the study will be stopped and undergo further review if ≥ 1 deaths or a serious AE directly related to calibration device use (i.e., stapling across device while creating sleeve gastrectomy or serious device malfunction leading to patient injury) occurs.

Safety reports will be sent to the MB for review after the first 5 subjects are enrolled and within 12 months of the study start date. Safety assessment reports will provide a

detailed analysis of safety issues including the incidence of AEs, clinical severity of AEs, serious AEs, UPs, deaths and protocol deviations. The PI will also document receipt and review of these safety reports in addition to any corrective actions and/or resolutions to findings reported which will also be reported to the IRB.

The sponsor does not have any additional reporting requirement than what Emory Hospital already has in place.

15. Economic Burden to Participants

N/A

16. Informed Consent Process

Consent will be obtained in person before the patient undergoes surgery by the principal investigator, co-investigators, and/or research study coordinator. Consent will likely occur at the initial surgical consultation, but may be obtained at any point prior to randomization. Patients will be notified if they are going to be in the EGD vs. ViSiGi device arm of the sleeve gastrectomy protocol during the perioperative period; it will be explained to them that this selection is being done in a randomized fashion, similar to flipping a coin, factoring in various patient-related factors. No elements of HIPAA will be waived. The study participants are legal adults and not pregnant, prisoners, or otherwise cognitively impaired in any way.

DocuSign:

The study team will use an Emory DocuSign account that is HIPAA compliant and meets the FDA's requirement for CFR Part 11 signatures. The consent process begins when a patient is screened and identified as eligible for study participation. A member from the study team will discuss the informed consent form in its entirety with the potential participant via telephone phone and/or Zoom. The patient's identity will be verified by requesting that he/she confirm their demographical information (i.e. full name, DOB, address, etc.).

In DocuSign, potential subjects have the ability to review the consent document as freely as they would if they were consenting in person. They also have the opportunity to exit the document without signing. The patient will be offered ample time to discuss the informed consent form with family and or friends, and have questions answered.

The process for obtaining final consent is outlined below:

1. First, the IRB-approved, stamped informed consent form(s) are added to an envelope in DocuSign.

- Secondly, recipients (subjects/coordinators) are then added to the envelope and signature and initial fields are assigned to them on the IRB approved informed consent form.

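### Two of the three weight-loss measures are the same number, and the third, %EWL, also depends on baseline BMI and on a reference weight that the plan does not state (minor)

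*Combined protocol and SAP*

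**What the plan says.** Section 2, secondary aim iii, item 2 lists the weight outcomes as "mean % total body weight loss, mean % EWL, mean % change in BMI", at 12 months with a window of 12 months either side. It gives no formula, no ideal or reference weight for %EWL, and no rule for which weight and height count as baseline. No measure is named as the lead.

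Section 13 sets the first analysis: "An initial approach will focus on a pairwise analysis (t-test) between the ViSiGi and EGD calibration groups for each of the primary and secondary aims". The next sentence there plans a broader multivariate analysis using demographic and clinical variables, without listing them. Section 5 describes the baseline demographic and clinical variables as "age, gender, race, BMI, smoking status, functional status, and medical comorbidities", so baseline BMI is collected and belongs to that group. Section 5 also gives the registry as a source of weight results, "MBSAQIP (30-day outcomes and weight loss outcomes"), and says that "the 12-month assessment time frame will be extended to 24 months post-surgery to help gather GERD-HRQL and weight loss data". Section 6 restricts entry to adults ("Patients selected for this study will be adults, 18 years old or older") and sets no BMI range.

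**The concern.** Height does not change in an adult over one to two years, so it cancels from percent change in BMI. What remains is percent total body weight loss. A results table with both would show one result in two rows, and a reader who does not notice may count it twice.

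%EWL is a different number, but the only thing it adds to %TBWL is the patient's starting BMI relative to a reference weight. Two patients who lose the same fraction of their weight get different %EWL values if they started at different BMIs. An unadjusted comparison of %EWL therefore carries extra variance that a variable already collected could remove. Because the reference weight is not stated, the %EWL values cannot be reproduced from the plan.

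What is at stake is clear reporting and some precision on one item of a secondary aim.

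**Working it through.** **Inputs.** From the documents: the three measures (Section 2), adult participants (Section 6), baseline BMI collected (Section 5), and 50 patients per arm with an initial t-test (Section 13). Not in the documents, so assumed: the reference weight, the baseline BMI distribution, the mean and SD of %TBWL, their correlation, and complete weight data on 50 per arm.

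**The plan's own figure.** The plan has no sizing figure for weight loss. Its only one is for staple firings: a difference of 0.4 with SD 0.7. Assuming two-sided 5% and 80% power, n = 2 × (1.96 + 0.84)² × 0.7² / 0.4² ≈ 48.1, so 49 per arm against the 50 planned. That figure reproduces, and nothing below affects it.

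**Step 1: percent change in BMI.** Let W0 and W1 be weight before and after, and h height.

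(W0/h² − W1/h²) / (W0/h²) = (W0 − W1) / W0 = %TBWL.

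The identity holds patient by patient, so mean loss, SD, confidence interval and two-sided p-value coincide (apart from sign, if change is recorded as negative). In 100,000 simulated adults the largest difference was 2 × 10⁻¹⁴ points, which is rounding. It requires one height and one baseline weight for both measures. A follow-up height 1 cm different would separate them by about 0.9 points, but that is measurement artefact.

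**Step 2: %EWL.** With the reference weight written as a BMI, R:

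%EWL = (W0 − W1) / (W0 − R·h²) = %TBWL × BMI0 / (BMI0 − R).

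At an identical 25% TBWL:

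| Baseline BMI | R = 22 | R = 23 | R = 25 |
|---|---|---|---|
| 35 | 67.3 | 72.9 | 87.5 |
| 40 | 55.6 | 58.8 | 66.7 |
| 50 | 44.6 | 46.3 | 50.0 |
| 60 | 39.5 | 40.5 | 42.9 |

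For example, 25 × 35/(35 − 25) = 87.5 and 25 × 60/(60 − 25) = 42.9. Down a column the change is due to baseline BMI alone. Across a row it is due to the unstated reference alone.

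**Step 3: size for a comparison of arms.** These are contrasts between single patients; arm means differ far less. Simulation with R = 25, BMI truncated below at 35, and %TBWL of mean 25, SD 8, independent of BMI:

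| Baseline BMI mean / SD | %EWL variance explained by BMI | By %TBWL | SE reduction = 1 − √(1 − share explained by BMI) |
|---|---|---|---|
| 44 / 4.5 | 14% | 83% | 7% |
| 46 / 6 | 17% | 79% | 9% |
| 48 / 7 | 18% | 77% | 10% |

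With a correlation of +0.2 or −0.2 between BMI and %TBWL, the share explained by BMI runs from about 4% to 32%.

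Under independence the slope is −1.3 to −1.8 %EWL points per BMI unit, and the standard error of a chance BMI imbalance at 50 per arm is about 0.85 to 1.3 units. A typical imbalance therefore moves the %EWL difference by about 1.6 to 1.7 points (1.84 × 0.85 ≈ 1.6; 1.30 × 1.30 ≈ 1.7), against a total standard error of about 3.9 to 4.2.

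**The case against.** The strongest reply is that Section 13 already plans a multivariate analysis with demographic and clinical variables, and Section 5 places BMI in that group. A reader might infer that baseline BMI goes unused; the documents do not support that. The gap that remains is one of specification: Section 13 neither names BMI nor fixes the model, and the adjusted analysis follows the t-test.

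Second, a reader might infer from the 87.5 versus 42.9 contrast that %EWL mainly reflects starting BMI. It does not. In the independence scenarios above, %TBWL accounts for roughly 77 to 83% of its variance. Arms averaging BMI 43 and 46, with equal 25% TBWL, would show about 59.7 versus 54.8 %EWL, and a 3-unit gap is itself more than two standard errors of chance imbalance.

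Third, a reader might infer that the unadjusted t-test is misleading. Under randomization, chance imbalance in BMI is part of the sampling error that the test already counts. In 20,000 simulated null trials (BMI mean 46, SD 6) it rejected 4.8% of the time at a nominal 5%.

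Fourth, Section 2 only lists the three measures. Nothing there calls them independent or corroborating, and two identical measures add no false-positive risk because they share one p-value.

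All four replies stand. They limit the consequence, but they do not remove the duplicate test or supply the missing reference weight.

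**Conclusion.** The point holds as a minor one. The duplication is exact algebra and rests only on using one height and one baseline weight per patient. That %EWL depends on baseline BMI and on R is also exact if the reference weight is set by a BMI.

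The size of that dependence is an assumption-based estimate: about 14 to 18% of %EWL variance, and a 7 to 10% smaller standard error after adjustment, under the distributions shown. The share widens to about 4 to 32% if BMI and %TBWL are modestly correlated. The loss is one of precision, not validity.

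No gain has been shown from adjusting %TBWL itself, because the main calculation takes it to be independent of BMI. This is one item of a secondary aim with no power claim attached, and no conclusion on staple firings depends on it.

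**What to change.** In Section 2, name %TBWL as the single lead weight-loss comparison and drop percent change in BMI as a separately tested outcome. State which weight and height count as baseline.

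If %EWL is kept, give its reference weight in Section 2. In Section 13, make its between-arm comparison a regression on arm with baseline BMI as a covariate, replacing the plain t-test for that outcome. Adjusting %TBWL in the same way would do no harm but is not needed on this evidence.

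The cost is a few sentences in Sections 2 and 13. No new data are required, because baseline BMI is already collected, and the sample size does not change.

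### Intra-operative cost has no rule for patients without a figure, and its administrative source may leave out the free ViSiGi device; cost each operated case from recorded quantities at fixed prices

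*Combined protocol and SAP*

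**What the plan says.** Secondary aim ii (section 2, Objectives) is to "Evaluate if there is a significant difference in operative duration (time) and intra-operative cost for patients undergoing EGD vs" the ViSiGi device. Section 13 (Statistical Analysis) gives the test: "An initial approach will focus on a pairwise analysis (t-test) between the ViSiGi and EGD calibration groups for each of the primary and secondary aims". The planned size is 50 per arm.

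The source of cost is listed in section 5, under post-operative data: "Cost data (administrative data) from internal databases". The role table in section 4 has two instructions about it, both in the 2-month column. The surgeon row says "obtain cost data", without a qualifier. The data analyst row says "GERD data entry, enter cost data as able". In that same analyst row, operative duration and stapler information are to be entered on the day of surgery with no such qualifier.

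No section defines intra-operative cost, sets a completeness target, names an analysis set for cost, or says how missing cost is handled. The allowance from 100 to 125 patients in section 13 is for screen failures, withdrawals and the like; missing cost is not mentioned.

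The funding row of the summary table says that the manufacturer provides the ViSiGi devices free.

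The intra-operative record in section 12 covers stapler type, number of firings, length of loads, "Number, order & color of stapler loads", reinforcement, calibration device, and whether an EGD was done.

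**The concern.** Saving money is one of the reasons given for the trial. The Background (section 3) names three sources of saving: fewer staple loads, less operating-room time, and no scope reprocessing. The cost comparison is where these should come together, and it has two weak points.

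First, a t-test uses whoever has a value. If cost is entered only when it can be had, the cost comparison may cover fewer patients than the comparisons of firings and time. If the chance of having a figure differs by arm and is related to cost, the comparison is also biased.

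Second, a device that the hospital did not buy may not appear in the hospital's cost record. The administrative comparison could then count what ViSiGi saves and leave out what it would cost to buy. Complete data would not cure this.

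Both are avoidable, because the quantities behind the three named sources of saving are already to be collected for each patient.

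**Working it through.** **1. The plan's own figure.** Inputs from section 13: difference 0.4 firings, SD 0.7, 50 per arm. Alpha and power are not stated; I assume two-sided 0.05 and 80%.

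- n per arm = 2 × (1.960 + 0.842)² × (0.7/0.4)² = 2 × 7.85 × 3.0625 = 48.1, so 49, against 50 planned.
- Power at 50 per arm: 0.4 / (0.7 × √(2/50)) = 2.857; Φ(2.857 − 1.960) = 81.5%.
- Enrolment: 100 / (1 − 0.20) = 125, as stated.

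The size reproduces, but for firings only and with little slack. No SD or target difference is given for cost.

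**2. Incomplete cost data.** The completeness rates are assumed. The standard error grows by √(50/n). The detectable difference at 80% power is 2.80 × √(2/n), in SDs of cost. The last column is power for an effect of 0.4/0.7 = 0.571 SD, the standardised effect used for firings.

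| Completeness | n per arm | SE ratio | Detectable difference (SD) | Power for 0.571 SD |
|---|---|---|---|---|
| 100% | 50 | 1.00 | 0.56 | 81.5% |
| 90% | 45 | 1.05 | 0.59 | 77.4% |
| 80% | 40 | 1.12 | 0.63 | 72.4% |
| 60% | 30 | 1.29 | 0.72 | 60.0% |

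**3. Selection.** If missing cases cost k SD more than observed ones, the arm difference shifts by k × (difference between arms in the proportion missing). With assumed completeness of 90% and 70%, and k from 0.5 to 1.0, the shift is 0.20 × 0.5 = 0.1 SD to 0.20 × 1.0 = 0.2 SD. With equal completeness and the same selection in both arms it is zero.

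**4. The free device.** If the administrative record carries no charge for ViSiGi, the difference in mean cost is wrong by the full purchase price, in favour of ViSiGi. The documents give no ViSiGi price. For scale, take the plan's 0.4 loads, its reprocessing estimate of about $200 (section 3), and an assumed load price of $150 to $350:

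- 0.4 × 150 + 200 = $260
- 0.4 × 350 + 200 = $340

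Before any saving in operating time, a device price in that range would cancel the whole saving. This shows how much the price matters; it does not estimate the price.

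**5. Would itemised costing be more precise?** Every price, minute rate and time SD here is assumed. Counting loads and time only, and treating them as independent, SD = √[(0.7 × load price)² + (minute rate × time SD)²].

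- Low: √[(0.7 × 150)² + (20 × 10)²] ≈ $226
- High: √[(0.7 × 350)² + (40 × 25)²] ≈ $1,030

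For administrative cost I assume an SD of $800 to $2,500. The 95% half-width at 50 per arm is 1.984 × SD × √(2/50): about $90 to $410 itemised, and about $320 to $990 administrative. The ranges overlap. Power for the $260 to $340 saving is 8% to 56% with administrative cost. At the high time and rate assumptions, itemised cost gives 25% (saving $260, SD $1,005) or 37% (saving $340, SD $1,030), below the best administrative case. A gain in precision is possible but not established.

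**The case against.** The conditional wording occurs once, in a staff task table and not in the analysis section. The surgeon row and the section 5 list ask for cost data without a qualifier. In a 2-month column, the phrase may only refer to when figures become available. No completeness rate is given. All of this stands, so a reader who infers that the cost test will run on a subset goes further than the documents do. What remains is that the conditional wording is in the instruction to the person who enters the data, and no rule covers a missing value.

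A reader might also infer that the administrative figure is noisy, includes items that calibration cannot affect, or drifts with prices. The documents do not describe its content, so they do not support this.

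Nor would itemised costing guarantee a value for every patient. Section 12 uses the structured template only where it is available, with the operative note as the alternative, and several items are free text. Against that, the coordinator is to see that the templates are completed, and the number of firings is the primary outcome, so it has to be captured anyway.

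Administrative costing is a legitimate choice. A cost built from recorded items is largely a weighted sum of firings and time, which are tested in their own right, and it does not itemise anaesthesia, staff or other disposables. That limits what it can claim. It does not answer the problem of the free device, which administrative costing may leave in place.

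**Conclusion.** The point holds as a change that should be made to a secondary outcome. The plan tests cost without defining it, without a rule for patients who lack a figure, and from a source that may omit the calibration device in one arm. The stronger ground is the free device: any omission biases the comparison by the full purchase price whatever the completeness.

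The loss from missing data is moderate under the assumed rates: a standard error 5%, 12% or 29% larger at 90%, 80% or 60% completeness, and a shift of 0.1 to 0.2 SD if completeness differs by arm and is related to cost as assumed. The dollar figures for power and precision rest on assumed prices and SDs. They do not show that the present cost comparison must fail or that itemised costing must be more precise. The case for the change rests on coverage of all operated patients and on pricing both arms alike. The analysis of firings is not affected.

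**What to change.** In section 13, define the main cost variable for all randomised and operated patients as recorded quantities multiplied by one price list fixed before analysis. The quantities are loads by type, reinforcement, calibration device, EGD use with scope reprocessing, and operative minutes. The list must give ViSiGi an explicit purchase price although the trial devices are free.

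State that this variable covers the sources of saving named in the Background and not all theatre inputs. Add a one-way price sensitivity table that varies the ViSiGi price. Keep administrative cost as a supportive analysis, with the number and percentage of patients who have it reported by arm. In the section 4 table, replace the conditional entry instruction so that the analyst and surgeon rows agree.

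The cost is one price list from hospital supply and operating-room finance, a short SAP paragraph and one table; no new patient data are needed. The downside is that the result depends on the chosen prices and on complete operative records, so gaps in those records should also be reported by arm.
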